### **5.2 Method of Assignment to Treatment**

A total of 64 participants will be randomized, 32 to receive placebo and 32 to receive deferiprone.

The sponsor will generate the randomization codes according to the study design. Once generated, the randomization codes will be final and will not be modifiable. An Interactive Voice (or Web) Response System (IVRS/IWRS) will be used to perform the randomization in this study.

### **5.3 Blinding Procedures**

The placebo solution will have the same appearance and flavor as deferiprone oral solution, and will be administered at a volume matching that required for a 25, 50, or 75 mg/kg/day dose of active product.

Sites will be provided with code-breaking instructions. In the event of an emergency, the randomization code may be broken only if knowledge of the respective treatment is necessary for adequate treatment of the emergency. The sponsor must be contacted within 24 hours in case of unblinding. Randomization information will be held by designated individual(s). The date and reason for breaking the blind must be documented.

### **5.4 Allocation of Patient Numbers**

After provision of informed consent (and assent if applicable), each patient will be assigned a unique ID number, and will be identified in all study data by this number rather than by name. The ID number will consist of 6 digits, where the first 3 digits represent the site code (001 for site #1, 002 for site #2, etc.) and the next 3 digits (separated from the first 3 by a hyphen) are assigned sequentially for each individual enrolled at that site. For example, if site #1 enrolls 8 patients, the ID numbers will be 001-001 to 001-008. The assigned ID numbers of patients who are screening failures or who withdraw from the study will not be reused.

### **5.5 Treatment Compliance**

Compliance will be determined as follows: 1) participants will use the daily diary card to record the amount of study medication administered, and 2) at each visit, the investigator or delegate will collect the medication containers, whether empty, partly used, or unopened, and will check the volume of solution remaining by weighing the bottles. Compliance will be calculated by the volume of solution taken divided by the volume of solution prescribed as per the dosing frequency and length of treatment. Any discrepancies must be discussed with participants and documented in the source documents. Reasons for non-compliance with the treatment will be recorded in the source document and in the eCRFs. The investigator should discuss treatment compliance at each visit.

If the volume of returned solution is less than it should be but the parent/guardian (or patient, as applicable) reports having administered or taken the correct amount of medication, the site will report compliance as 100% in the eCRF, and will provide the reason for the apparent over-compliance (e.g., solution was accidentally spilled), along with the actual percentage. Both under-compliance < 80% and over-compliance >120% will be reported as a protocol deviation, unless under-compliance is due to treatment interruption because of infection or neutropenia or other extenuating circumstances (see [Section 7.2.1.8](#)).

## **6 STUDY TREATMENTS**

Patients will receive either deferiprone oral solution 80 mg/mL or matching placebo solution.

### **6.1 Investigational Product**

Deferiprone oral solution (3-hydroxy-1,2-dimethylpyridin-4-one) is manufactured by Apotex Inc., and will be supplied to the clinical sites by ApoPharma Inc.

The 80 mg/mL formulation used in this study is a clear reddish solution with a bubble gum-flavored aroma.

#### **6.1.1 Dosage Form and Mode of Administration**

Deferiprone oral solution is to be administered orally, using a syringe, three times a day. It can be given with or without food, as per the investigator's recommendation.

#### **6.1.2 Precautions for Use**

Deferiprone oral solution 80 mg/mL is to be stored at 15–30°C in the container in which it is supplied. Bottles should not be stored in direct light.

### **6.2 Reference Product**

The placebo product will be matched to deferiprone oral solution for color and flavor, and will be provided in the same type of bottle and with the same label.

### **6.3 Packaging and Labeling**

The product will be supplied in 250 mL amber-colored bottles with child-resistant closure and a tamper-evident seal. The containers will be provided with labels whose content is in accordance with all applicable regulatory requirements and includes details such as protocol number, expiry date, lot/batch number, investigational statement, storage temperature, dosage, direction for use, visit number, date dispensed, and name and address of the study sponsor.

### **6.4 Shipping and Storage**

The study medication at each site will be kept in a secure location (a locked room or cabinet) under adequate storage conditions, as per label requirements, under the control of the investigator and with access to authorized individuals only. Product is to be kept at room temperature (15–30 °C / 59–86 °F). The room must have a calibrated digital temperature-monitoring device, and daily recordings of the storage facility temperature must be available. Temperature excursions must be immediately reported to the sponsor for investigation and determination of impact on the study medication.

A receipt form will be provided to the study sites by the sponsor with each shipment of investigational product. The investigator or a designee is to sign and date this receipt form to acknowledge receiving the entire product shipment in good condition, and to record the time at which the temperature-monitoring device was removed and stopped. The site will fax or email a copy of this receipt form to the sponsor and retain the original in its Investigator Trial File.

## 6.5 Product Accountability

The investigator must maintain an updated Site Investigational Drug Inventory Record at the study site. This log will include at a minimum:

- Name of sponsor
- Name of investigator
- Study identifier
- Date and quantity of investigational product received from sponsor
- Lot/batch number

For each patient, the investigator must maintain an updated Patient Investigational Drug Dispensing Record. This log will include at a minimum:

- Patient identification number
- Date of dispensing and return
- Dispenser's initials
- Quantity dispensed and returned

At the conclusion of the study, a final inventory must be performed by the investigator (or delegate). If any bottles are missing, this must be indicated on the study drug accountability form, together with an explanation of the discrepancy. These forms must be available for sponsor clinical monitoring as well as for sponsor audit and regulatory authority inspection purposes at any time.

It is the responsibility of the investigator to ensure that all study drug received at the site is inventoried and accounted for throughout the study. Records of receipt, storage, and administration of the study drug supplied must be maintained, and the drug accountability will be verified by the sponsor or sponsor's designee during on-site monitoring visits. The sponsor will be responsible for determining the specific conditions for destruction of unused product.

## **6.6 Replacement Doses**

If medication has been lost or damaged, participants will need to return to the study site to receive replacement bottles. Requests for replacement must be made in writing to the sponsor by the qualified staff member. All information related to the lost or damaged medication and the replacement medication is to be recorded in the drug accountability forms and patient source data.

## **6.7 Disposition of Unused Product**

All investigational product that has been returned by participants or that is unused for any other reasons will be returned to the sponsor or discarded by the site according to internal procedures, if approved, in writing, by the sponsor. The destruction procedures must include the issuance of appropriate signed destruction certificates including mode of destruction and complete drug accountability of destroyed materials. The destruction may take place only after written approval by the sponsor.

## **6.8 Other Study Supplies**

All required study supplies, including but not limited to diary cards and laboratory kits, will be provided by the sponsor to the sites.

# **7 MEASUREMENTS AND EVALUATIONS**

## **7.1 Efficacy Measurements**

Efficacy will be measured by monitoring levels of serum ferritin, transferrin saturation, and labile plasma iron.

### **7.1.1 Serum Ferritin**

Ferritin is a protein that stores iron in a non-toxic form, transports it to areas where it is required, and releases it in a controlled manner, thereby acting as a buffer against iron deficiency and iron overload. It is mainly found in tissues, but small amounts are secreted into the serum, where it can serve as an indirect but easily measurable marker of the total amount of iron stored in the body. (Drawbacks of using it as a marker include lack of specificity, as disorders other than iron overload can cause large amounts of ferritin to be released into the circulation, and inter-patient variability.) Levels of serum ferritin above 1000 ng/mL are often considered to be associated with iron toxicity. In young children who have only recently begun an RBC transfusion regimen, it takes some time for this level to be reached, but in the absence of chelation it inevitably is reached.

Serum ferritin will be measured at each visit, and the time to reach a level  $\geq 1000 \mu\text{g/L}$  will be compared between the treatment arms.

### **7.1.3 Labile Plasma Iron**

Labile plasma iron is a component of NTBI, and is the most toxic form of iron since it acts as a catalyst in the formation of harmful free hydroxyl radicals which can damage cellular DNA, proteins, and membrane lipids. High levels of this form of iron may be found in individuals with conditions of iron overload. As this measure is highly variable, the blood samples for its assessment will always be collected at approximately the same time of day and at approximately the same amount of time after the last dose of study medication, in an attempt to decrease variability as much as possible.

Labile plasma iron will be measured at each visit, and the time to reach a level  $\geq 0.6 \mu\text{M}$  will be compared between the treatment arms.

## **7.2 Safety Measurements**

### **7.2.1 Medical Events, Adverse Events, and Serious Adverse Events**

#### **7.2.1.1 Definition of Medical Events and Adverse Events**

*Medical Event (ME):* Any new untoward medical occurrence or worsening of a pre-existing condition in a clinical trial participant that occurs after signing the informed consent form (ICF) but before receiving the first dose of study drug.

*Adverse Event (AE):* Any untoward medical occurrence in a patient who is administered a pharmaceutical or other therapeutic product in a clinical study, not necessarily having a causal relationship with the product. An AE can therefore be any unfavorable and unintended sign, symptom, or disease temporally associated with the use of a product, whether or not considered related to that product.

AEs include:

- Exacerbation of a pre-existing illness, including acute episodes/crisis of a chronic underlying condition
- An increase in frequency or intensity of a pre-existing episodic event or condition
- A condition detected or diagnosed after study treatment administration, even though it may have been present prior to the start of the study
- A continuous persistent disease or symptom present at baseline that worsens following the start of the study
- Accidents (e.g., involving a motor vehicle)
- Reasons for changes in concomitant medication (type of drug and/or dose)
- Medical, nursing, or pharmacy consultation
- Admission to hospital and surgical operations
- Abnormalities in laboratory findings (e.g., clinical chemistry, hematology, urinalysis), other assessments (e.g., vital signs) that are not part of a larger medical condition already recorded as an AE and which are judged by the investigator to be clinically significant. The investigator should exercise medical and scientific judgment in deciding whether an abnormal laboratory finding or other abnormal assessment is clinically significant.

AEs do not include:

- A pre-existing disease or condition present or detected at the start of the study that does not worsen
- Hospital admissions or surgical procedures that had been planned prior to enrolment into the study
- The disease or disorder being studied, or a sign or symptom associated with that disease or disorder, unless it has worsened
- An overdose of either the study treatment or concurrent medication without any signs or symptoms

#### **7.2.1.2 Monitoring and Documenting of Medical Events and Adverse Events**

Prior to enrolling a patient, study site personnel will note the occurrence and nature of any medical condition(s) in the source documents and the appropriate section of the eCRF. During the study, they will note any change in the condition(s), and the occurrence and nature of any MEs/AEs. MEs will be collected from the time the ICF is signed until the first dose of study drug, and AEs will be collected from the time the treatment starts until 30 days

after the last dose.

AEs and SAEs that are related to the underlying medical condition for which the patient enrolled in the clinical trial will be recorded separately from others.

Participants will be instructed to report any MEs/AEs to the investigator or a delegate. In addition, the investigator will solicit information about the occurrence of MEs/AEs through open-ended, non-leading verbal questions such as:

- How is your child feeling?
- Has your child had any medical problems since the last visit?
- Has your child taken any new medications, other than those provided in this study, since the last visit?

Based on the responses to these questions, the investigator or delegate should ask additional questions relevant to the specific complaint, such as:

- How severe is/was the symptom?
- How often did the symptom occur?
- How long did the symptom last?

Participants should also be questioned about any previously reported AEs that have not resolved.

The investigator will evaluate all AEs/MEs for their relationship to the investigational product ([Section 7.2.1.3](#)), intensity ([Section 7.2.1.4](#)), and seriousness ([Section 7.2.1.5](#)), and will document any measures taken to address the event. There should be an attempt to establish a diagnosis of the AE based on signs, symptoms, and/or other clinical information. Wherever possible, a diagnosis should be documented, rather than the individual signs/symptoms. All information is to be clearly recorded in the source documents.

If the dosage of study drug is reduced or treatment is discontinued as a result of an AE, the circumstances leading to such reduction or discontinuation must be clearly documented.

All AEs must be followed until resolution, the condition stabilizes, the event is otherwise explained, or the patient is lost to follow-up. The investigator is responsible for ensuring that follow-up includes any supplemental investigations that are needed to elucidate the nature and/or causality of the AE as completely as possible. This may include additional laboratory tests or investigations, histopathological examinations, or consultation with other health care professionals.

### 7.2.1.3 Assessment of Causality

The relationship of an AE to the study drug should be determined by the investigator after thorough consideration of all available facts, including associative connections (time or place), pharmacological explanations, previous knowledge of the drug, presence of characteristic clinical or pathological phenomena, exclusion of other causes, and/or absence of alternative explanations. The causal relationship of an adverse event to study drug will be assessed according to the following criteria (based on World Health Organization definitions):

- Not related: Temporal relationship to study drug administration is missing or implausible, or there is no evident cause.
- Possibly related: Reasonable time sequence to administration of study drug, but event could also be explained by concurrent disease or other drugs or chemicals.
- Probably related: Reasonable time sequence to administration of study drug, and unlikely to be attributed to concurrent disease or other drugs or chemicals, and follows a clinically reasonable response on withdrawal (de-challenge). Re-challenge information is not required.
- Definitely related: Plausible time relationship to study drug administration, and cannot be explained by concurrent disease or other drugs or chemicals. The response to withdrawal of the drug (de-challenge) should be clinically plausible. The event must be definitive pharmacologically or phenomenologically, using a satisfactory re-challenge procedure if necessary.

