### 7.2.1.6 Reporting of Serious Adverse Events

All SAEs occurring up to 30 days following completion of or discontinuation from the study must be reported to the sponsor, regardless of whether they are suspected of having a causal

relationship with the study drug. Any SAEs for which the investigator does suspect a causal relationship must be reported to the sponsor regardless of the time elapsed since the last dose of the study drug.

Participants will be instructed to report SAEs to the investigator **within 24 hours**, by telephone. In turn, the investigator must report all SAEs to the sponsor **within 24 hours** of occurrence or notification by the participant, using the sponsor's SAE form. The sponsor will provide contact information for reporting SAEs. An assessment of causality must be provided at the time of the initial report. The investigator or delegate must then complete and submit a follow-up SAE form to the sponsor **within 5 calendar days**, and must submit further follow-up forms if additional relevant follow-up information becomes available.

The sponsor will submit reports of SAEs to the appropriate regulatory agencies, in line with local regulatory requirements and timelines.

Investigators must report all SAEs to their IRB/IEC as well as to the sponsor. If any SAE that is considered at least possibly related to the study medication and is unexpected occurs at one site, the sponsor will promptly inform all other sites of this, and all investigators must then report this event to their own IRBs/IECs, following the same timelines as above or following local IRB/IEC policy, whichever takes precedence.

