## 8 STUDY COMMITTEES

An independent Data Safety Monitoring Board (DSMB) will be established to monitor the safety of patients during the course of the study. Members of the DSMB will be responsible for overseeing the conduct of the trial, and will be empowered to recommend stopping the trial if, in their judgment, continuation is not ethically acceptable on the grounds of safety.

Death or a life-threatening event in any study patient which is deemed by either the investigator or the sponsor to be at least possibly related to the study medication will trigger an evaluation by the DSMB for recommending stopping the study. Details will be provided in the DSMB charter. No study-stopping decision will be made without prior consultation with the sponsor.

The operating model and the frequency of the interim safety review meetings will be laid out in the DSMB charter. The DSMB will be constituted prior to the enrolment of any patients into the study, and its members will be notified of any changes to the protocol or the study conduct. The DSMB will be informed of any substantive changes to the protocol that could affect patient safety prior to their implementation.

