## 14.3 Safety analyses

### 14.3.1 Adverse events

Table 14.3.1.1 Overall summary of adverse events

	Deferiprone	Placebo	
N	xxx	xxx	P-value
Number of patients experiencing at least one AE	xx (xx%)	xx (xx%)	0.xxxx
Number of patients experiencing at least one severe AE	xx (xx%)	xx (xx%)	0.xxxx
Number of patients experiencing at least one serious AE	xx (xx%)	xx (xx%)	0.xxxx
Number of patients experiencing at least one related* AE	xx (xx%)	xx (xx%)	0.xxxx
Number of patient deaths	xx (xx%)	xx (xx%)	0.xxxx
Number of patient withdrawals due to AEs	xx (xx%)	xx (xx%)	0.xxxx

\*Includes possibly, probably, and definitely related. Worst case scenario of causality between the investigator and company's assessment.

Data source: 16.2.7.2 Listing of adverse events

Table14.3.1.2 Adverse events

	Deferiprone (N=xx)	Placebo (N=xx)	Fisher's exact test
	Exposure (Patient-years):x.xx	Exposure (Patient-years):x.xx	
	Total Events: xxx	Total Events: xxx	
System Organ Class Preferred Term	n Patients (%)	n Patients (%)	p-value
CCCCCCC	x (x.x)	x (x.x)	0xxxx
Ccccccc	x (x.x)	x (x.x)	0xxxx
Ccccccc	x (x.x)	x (x.x)	0xxxx
Ccccccc	x (x.x)	x (x.x)	0xxxx
.....	.....	.....	.....

Data source: 16.2.7.2 Listing of adverse events

Note: Similar Table 14.3.1.2 to Table 14.3.1.11 will be produced.

Table 14.3.1.12 Adverse events by causality

		Deferiprone (N=xx)	Placebo (N=xx)
System Organ Class Preferred Term	Relatedness (worst case)	Patients reporting (n=xx)	Patients reporting (n=xx)
CCCCCCCC		x (x.x)	x (x.x)
ccccc	Not Related	x (x.x)	x (x.x)
	Related*	x (x.x)	x (x.x)
cccccc	Not Related	x (x.x)	x (x.x)
	Related*	x (x.x)	x (x.x)
.....	.....	.....	.....

\*Possibly, Probably, or Definitely Related

Data source: 16.2.7.2 Listing of adverse events

Table 14.3.1.13 Adverse events – event count and rate

System Organ Class Preferred Term	Deferiprone (N=xx)	Placebo (N=xx)
	Exposure (Patient-years):x.xx	Exposure (Patient-years):x.xx
	Total Events (Rate/100 patient- years): xx (x.xx)	Total Events (Rate/100 patient- years): xx (x.xx)
CCCCCCC	xx (x.xx)	(x.xx)
Cccccc	xx (x.xx)	xx (x.xx)
Ccccccc	xx (x.xx)	xx (x.xx)
Ccccccc	xx (x.xx)	xx (x.xx)
.....	.....	.....

Data source: 16.2.7.2 Listing of adverse events

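### The causality scale rates events with no evident cause as Not related, so a well-timed, unexplained event without de-challenge data fits no related category

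*Protocol*

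**What the plan says.** Protocol section 7.2.1.3 holds the only causality scale in the two documents. The SAP adds none, and its section 4.2.1 refers back to protocol section 7.2.1 for the event definitions. The lead-in lists what the investigator should consider, including "previous knowledge of the drug, presence of characteristic clinical or pathological phenomena, exclusion of other causes, and/or absence of alternative explanations". Four categories follow:

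- The lowest reads "Not related: Temporal relationship to study drug administration is missing or implausible, or there is no evident cause".
- *Possibly related* reads "Reasonable time sequence to administration of study drug, but event could also be explained by concurrent disease or other drugs or chemicals".
- *Probably related* needs reasonable timing, and the event must be "unlikely to be attributed to concurrent disease or other drugs or chemicals, and follows a clinically reasonable response on withdrawal (de-challenge".
- *Definitely related* needs plausible timing, no other explanation, a clinically plausible response to withdrawal, and an event that is definitive on pharmacological or phenomenological grounds.

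The rating is then used in four places:

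- **Drug reaction counts.** The footnote to SAP Table 14.3.1.1 defines related as "Includes possibly, probably, and definitely related" and takes the "Worst case scenario of causality between the investigator and company's assessment".
- **Cross-site alert (protocol 7.2.1.6).** The condition is "If any SAE that is considered at least possibly related to the study medication and is unexpected occurs at one site".
- **Late SAEs (same section).** Beyond 30 days after completion or discontinuation, an SAE has to be reported only if the investigator suspects the drug.
- **DSMB trigger (protocol section 8).** It applies to a death or life-threatening event "deemed by either the investigator or the sponsor to be at least possibly related to the study medication".

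**The concern.** The second limb of *Not related* appears to be inverted. When an event follows dosing at a plausible interval and nobody can find a cause for it, the drug has not been ruled out. The scale nevertheless lets the lack of a known cause settle the matter against a relationship.

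Safety and tolerability are the trial's secondary objective, in children from 6 months of age, and relatedness is a listed attribute of the AE and SAE endpoints. Two investigators who both follow the text could rate the same event in opposite ways. The events most exposed are new or unexplained ones, which the cross-site alert exists to circulate, and fatal ones, where a response to withdrawal is least likely to be available.

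**Working it through.** The plan states no figure on this point, so the check is textual: sort events by the three features that the definitions use, and see which categories each combination meets.

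| Timing | Alternative explanation | Favourable de-challenge | Categories whose wording is met |
|---|---|---|---|
| Implausible or missing | Either | Either | *Not related* (first limb) |
| Plausible | Yes | Either | *Possibly* |
| Plausible | None | Yes | *Probably*, or *Definitely* if also definitive; and *Not related* (second limb) |
| Plausible | None | No, or not available | *Not related* (second limb) only |

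**Third row.** The absence of another explanation supports a relationship under *Probably* and *Definitely*, and rules one out under the second limb. The section does not say which prevails.

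**Fourth row.** *Possibly* does not fit, because it describes an event with a competing explanation. *Probably* and *Definitely* do not fit, because both call on the response to withdrawal. Examples are a fatal event, an event that does not recover, and an event during which the drug was continued.

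**Second row.** A well-timed event plainly caused by something else lands in *Possibly*, because *Not related* has no limb for it. This supports reading the second limb as a slip for another evident cause, though the documents do not say so.

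Next, what a *Not related* rating by the investigator does in each place:

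1. **ADR and SADR counts** (SAP Tables 14.3.1.5 to 14.3.1.7, 14.3.1.10 and 14.3.1.11, and the related-AE row of 14.3.1.1). The event is omitted only if the company also rates it not related. This assumes that the worst-case footnote to Table 14.3.1.1 governs the other tables too.
2. **Cross-site alert.** The event must be related and unexpected. The section does not say whose rating counts, so a second rating is not assured.
3. **SAEs after 30 days.** The duty to report rests on the investigator's suspicion alone. If the event is not reported, the sponsor has nothing to re-rate.
4. **DSMB trigger.** It covers deaths and life-threatening events only, and fails only if neither the investigator nor the sponsor rates the event at least possibly related.

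In 1 and 4 the second rating protects only if the sponsor departs from the literal wording, and no other scale is provided.

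**The case against.** The strongest reply is that the main safeguards do not depend on causality. Every SAE up to 30 days goes to the sponsor whatever its rating. All AEs and SAEs are tabulated by arm, and in a randomised, blinded, placebo-controlled trial that comparison needs no attribution of individual events. The DSMB holds interim safety reviews and may recommend stopping on its own judgment; section 8 does not make the trigger its only route. All of this stands, and it limits the damage.

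A second reply is that the lead-in asks for judgment, so a sensible investigator would not apply the limb literally and might regard the drug itself as the evident cause. The rule on late SAEs likewise turns on suspicion, not on a category. This is fair, but an investigator who reasons that way in the fourth row finds no related category whose wording fits. The gap stays.

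A reader might go further in three ways that the documents do not support:

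- **That agranulocytosis would be hidden.** The protocol names it as the drug's most serious associated event and lists it as a reaction in Table 1.1 (18 of 860, 2.1%), so the drug is an evident candidate cause. Section 7.2.1.8.1 stops treatment at the first count below 0.5 x 10^9/L and requires notification on the SAE form, so de-challenge information will usually exist. As a listed reaction it would ordinarily count as expected (the protocol does not define the term), so the cross-site alert might not apply even if it were rated related. The pooled rate also says how often the reaction occurs, not how often an event would be misrated.
- **That unexplained events drop out automatically.** The worst-case and either-party rules mean that two ratings must fail for the counts and the DSMB trigger.
- **That every relatedness table loses these events.** The shell for Table 14.3.1.12 has separate rows for not related and related events, so an event rated *Not related* is still shown there.

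**Conclusion.** The wording is wrong as it stands. The limb on no evident cause contradicts the lead-in and the two upper categories of the same section, and it leaves one kind of event, well timed, unexplained and without usable de-challenge, with *Not related* as the only category whose wording it meets. Such an event can be left out of the ADR and SADR counts, the cross-site alert, late SAE reporting and the DSMB trigger. For the counts and the trigger, the sponsor would have to rate it not related as well. The alert and late reporting have no such assured second rating.

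The effect is confined to attribution. No efficacy endpoint, all-AE or SAE table, or SAE report within 30 days changes. Its size cannot be given as a number, because the documents do not show how many events would fall in the gap. The conclusion assumes that assessors apply the definitions as written and that no separate guidance outside these documents corrects them.

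**What to change.** In protocol section 7.2.1.3:

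- Change the second limb of *Not related* to 'or there is another evident cause'. The boundary with *Possibly related* then lies between a cause that is evident and one that merely could explain the event.
- State that *Possibly related* also covers reasonable timing with no alternative explanation when de-challenge information is lacking.

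Issue the corrected definition to the sites and to the sponsor's own assessors, so that both ratings rest on the same text.

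The SAP already describes visits that have taken place, so new wording alone will not reach existing ratings. Before database lock, and blinded to treatment, the sponsor should re-check well-timed AEs rated *Not related* for which no alternative cause is documented. The search should use timing and documented alternatives, because the documents do not say that the ground for a rating is recorded.

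The cost is a short protocol clarification and one blinded review of a subset of AEs. ADR counts may rise slightly in both arms. No dose, schedule or treatment rule is affected.
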